## **SCHEDULE AND EXPECTED COMPLETION DATE.**

The study will be carried out between october 2023 and june 2024.

## **ETHICAL-LEGAL ASPECTS**

All data collected will be managed in accordance with the regulations established by Organic Law 3/2018, of December 5, on the Protection of Personal Data and guarantee of digital rights; such as 14/2007 of July 3, on Biomedical Research; such as the Standards of Good Clinical Practice, Declaration of Helsinki, as well as the Oviedo Convention.

The study protocol and all associated documentation will be submitted for evaluation to the CAEI of Galicia. Any modification to the initial approved protocol will be sent for re-evaluation.

Researchers assume the commitment to make public the results of their research, whether positive or negative.

Since this is an anonymous survey, informed consent will not be necessary.

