## **ABSTRACT**

### **• PROTOCOL TITTLE**

Prospective observational study on the analgesic effectiveness of blocking the shoulder's anterior capsule and the suprascapular nerve by the anterior approach versus blocking of the suprascapular and axillary nerves by the posterior approach in shoulder arthroscopy.

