## **STUDY HYPOTHESES**

Two analgesic strategies included within the usual clinical practice will be compared for postoperative pain control after shoulder arthroscopy. With this study we want to compare the ultrasound-guided block of the suprascapular nerves and the shoulder joint capsule via the anterior route versus the ultrasound-guided block of the suprascapular and axillary nerves via the posterior route.

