## **STUDY TYPE**

An observational study of paired cohorts, not randomized, is designed in two hospitals in northern Spain in the period between october 2023 and september 2024.

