## PROTOCOL

All patients will be trained preoperatively in pain assessment using a Numerical Rating Scale (NRS) from 0 (absence of pain) to 10 (maximum pain endured). All patients will receive the same anesthesia and analgesia protocol; fentanyl, propofol and rocuronium prior to intubation.

Anesthetic maintenance with 1 MAC of sevoflurane and boluses of muscle relaxant and fentanyl if there is an increase >20% in blood pressure or above baseline heart rate. The anesthetic protocol will include analgesia with 1 g of paracetamol and 50 mg of dexketoprofen every 8 hours and a bolus of 0.1 mg/kg of intravenous dexamethasone. When the patient reports an NRS > 3 and functional impact, intravenous morphine will be administered at a dose of 0.04 mg/kg every 10 minutes until NRS < 3 in the PACU and tramadol 1 mg/kg in the ward. The nursing staff and the anesthesiologist in charge of the PACU will be blind to the block received by the patient in each study group.

Before general anesthesia, patients will be assigned to one of the study groups depending on the anesthesiologist responsible for performing the blocks.

**SHAC + SSN Group (anterior approach):** with the patient in the supine position and the arm placed in abduction and slight external rotation the ultrasound probe will be positioned in the transverse axis between the coracoid process and the humeral head. After identifying the tendon of the subscapularis muscle, a puncture will be performed in a lateral to medial plane and the local anesthetic will be deposited at two levels; one deep to the subscapularis tendon at the pericapsular level of the glenohumeral joint (5 ml of ropivacaine 0.2%), and another in withdrawal at about the level of the fascia that separates the subscapularis and deltoid muscles at a more superficial level (10 ml of 0.2% ropivacaine). Subsequently, the ultrasound probe will be positioned in the transverse axis at level with the neck to locate the suprascapular nerve through an anterior approach as it ran beneath the omohyoid muscle. After hydrodissecting the correct plane with saline solution 5 ml of 0.2% ropivacaine will be administered, depositing the local anesthetic under the lower belly of the omohyoid muscle.

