## **MATERIAL AND METHODS**

### **1.1 Definition of study subjects**

The inclusion criteria: being over 18 years of age, ASA physical status I – III and having been scheduled for shoulder arthroscopy surgery.

The exclusion criteria: any contraindication for performing regional anesthetic techniques (infection at the puncture point, alteration of hemostasis, allergy to local anesthetics, patient refusal to participate in the study, inability to evaluate postoperative pain, known neuropathy of the operated limb and patients who required conversion to open surgery).

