## **RISKS.**

Participation in this study does not imply an increased risk since it is a cross-sectional study, which will not interfere with the daily activities of the center in terms of clinical and therapeutic management of patients. The study will be carried out in accordance with local regulations and applicable laws and following internationally accepted ethical standards.

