## **CONFIDENTIALITY OF THE INFORMATION COLLECTED IN THE CONTEXT OF THE STUDY.**

The study research staff will ensure that the pseudonymization of participants is maintained. Which will be identified through a code in the electronic database, with all their information associated with this code and not with their personal data. This database will be stored on a service computer, access to which is password protected. Additionally, the database will also be protected by a password. This information will be stored securely and will only be accessible to members of the research team and authorized personnel.

The questionnaire to obtain the data will use the Microsoft Form platform and when the information is provided to the research team it will be coded and pseudonymized, making it untraceable and respecting the privacy of the data provided.

The person responsible for the processing and custody of the data will in all cases be the principal investigator of the study.

At the end of the study, the data will be stored in the institutional online repository of the Department of Health and Sergas RUNA for a minimum of 10 years, under a password that only the main researcher will have access to in Excel format that will be protected with a different password. also with only access for the main researcher.

In the future, if these data are required for subsequent studies, consent must be sought from the principal investigator.

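### The protocol omits informed consent by calling the study an anonymous survey, which is not the study it describes: a prospective, pseudonymised cohort comparison of two nerve blocks

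*Combined protocol and SAP*

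**What the plan says.** The section on ethical and legal aspects states: "Since this is an anonymous survey, informed consent will not be necessary". It gives no other reason for omitting consent. The same section commits the study to Good Clinical Practice, the Declaration of Helsinki and the Oviedo Convention. It says the protocol will go to the regional ethics committee and that later modifications will be sent for re-evaluation.

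The risk section says that taking part adds no risk "since it is a cross-sectional study" and does not interfere with clinical management.

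Elsewhere the study is described differently:

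- The title in the abstract begins "Prospective observational study on the analgesic effectiveness of blocking the shoulder's anterior capsule and the suprascapular nerve by the anterior approach versus blocking".
- The study type section reads "An observational study of paired cohorts, not randomized, is designed in two hospitals in northern Spain".
- The section headed Protocol says that before general anaesthesia "patients will be assigned to one of the study groups", according to which anaesthesiologist performs the blocks. It prescribes one anaesthesia and analgesia regimen for everyone.
- The confidentiality section says research staff will "ensure that the pseudonymization of participants is maintained" and that each participant's information is held under a code.
- Section 1.1 lists "patient refusal to participate in the study" among the exclusions.

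**The concern.** The rule on consent depends wholly on a description of the study. If that description is wrong, the rule has no stated basis. Here both halves of it look wrong: the study does not appear to be a survey, and the data do not appear to be anonymous. The risk statement has the same weakness, because it leans on a cross-sectional label that a cohort followed for 24 hours does not carry.

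What is at stake is patient protection. Followed as written, the ethics section lets patients enter a comparison of two invasive techniques without informed consent, for a reason that is not true of the study. An ethics committee weighing consent needs an accurate account of what is done to participants and what is kept about them. The eligibility section adds a practical difficulty: staff are told to exclude people who refuse, but are not told that anyone must be asked.

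**Working it through.** No arithmetic applies, since the point contains no figure and the plan gives none to reproduce. The check is to set each word of the stated ground, and the related risk label, against the rest of the protocol.

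**1. Is it a survey?**
- The title and study type section describe a prospective, non-randomised cohort study in two hospitals that compares two block techniques.
- The section headed Protocol assigns each patient to a group before general anaesthesia, fixes a common anaesthesia and analgesia regimen, and keeps recovery-unit staff blind to the block received.
- The section on variables evaluated records, for each patient, pain scores, opioid use, sensory and motor block, adverse effects and satisfaction.
- These are clinical outcomes after a procedure. An online form is used to capture data, but that is a collection tool and does not turn the study into a survey.

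**2. Is it anonymous?**
- The confidentiality section uses the language of pseudonymisation and says each participant is identified in the database by a code.
- Coded data are not anonymous data. The same section also calls the data untraceable, so it disagrees with itself.
- Pain is scored once before surgery and four times afterwards (1, 2, 12 and 24 hours), which is 1 + 4 = 5 scores per patient. To be analysed as planned, these must be attached to the block received, which fits coded records.

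**3. Is it cross-sectional?**
- Measurement runs from before surgery to 24 hours after it, at five time points. That is follow-up of a cohort over time.
- The no-added-risk statement therefore gives a design reason that does not hold.

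**4. Does the refusal exclusion fit with omitting consent?**
- Section 1.1 excludes patients who refuse to participate. Refusal presupposes some approach to the patient.
- The ethics section says consent is unnecessary, and no section available for review says how refusal is sought or recorded.
- The two are in tension. They could coexist if patients were informed verbally or could opt out, but the protocol does not say so.

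**Result.** Both parts of the consent ground (survey, anonymous) and the risk section's label (cross-sectional) are contradicted by other sections. The refusal exclusion is not reconciled with the consent sentence.

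**The case against.** The strongest reply is that the study is observational and close to routine care. The hypotheses section says: "Two analgesic strategies included within the usual clinical practice will be compared for postoperative pain control after shoulder arthroscopy". The group follows from the responsible anaesthesiologist and not from randomisation. The risk section says clinical management is not interfered with, and a questionnaire platform is used, which may be where the word survey came from. The ethics committee receives the whole protocol, so it would see the true design next to the consent sentence.

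Much of this is fair as context, and it might support a waiver on some other ground. It does not make the stated ground true. The usual-care picture is also less than complete: the background section says only anatomical work and small case series have been published on the anterior capsular block, and the recruitment section speaks of continuing until a set number is reached in each group. The protocol says it will be submitted, but mentions no waiver granted by the committee.

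A reader might infer several stronger points. The documents do not support them:

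- **That the data would be unusable, or the question unanswerable.** This depends on what the committee decided, on what ground, and on what the law requires. None of that is in the documents, and a consent defect does not by itself stop a dataset from answering a statistical question.
- **That unrecorded refusals bias the comparison.** If nobody is asked, there are no refusals. If some patients are asked, nothing links refusal to block group, so neither a bias nor its direction is shown.
- **That no patient is told anything.** The refusal exclusion suggests some contact. Consent pages were removed from the copy reviewed and the annexes show no content, so the absence of a form or information sheet proves nothing.
- **That consent must come before the group is known.** The documents give no reason to require that timing.

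**Conclusion.** The point holds as a contradiction in an operative rule. The only reason given for omitting informed consent is untrue of the study described, and the risk statement relies on a second wrong label. The consent sentence governs every participant, so this is more than a slip of wording and should be corrected. No estimate, test or sample size changes.

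The conclusion rests on the current text of the protocol alone. It assumes that the confidentiality section's account of coded, pseudonymised records is what will be done, despite its remark that the data are untraceable. It does not claim that consent is legally required, nor that a waiver could not be justified on a different ground, because the documents settle neither question.

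**What to change.** 1. Delete the anonymous-survey ground from the ethics section and the cross-sectional label from the risk section.
2. Then do one of two things. Either take informed consent and describe how, or request a waiver from the ethics committee on the true description: prospective, pseudonymised, group assigned by the responsible anaesthesiologist, 24 hours of follow-up. The ethics section already provides for re-evaluation of modifications, so the route exists.
3. Make the Protocol section, section 1.1, and the ethics, risk and confidentiality sections agree. This includes choosing between pseudonymised and untraceable in the confidentiality section.
4. If refusal remains an exclusion, state how it is sought and count the refusals.

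The cost is an amendment to the ethics committee and either a consent procedure or a reworded waiver request. If consent is taken, a few patients may decline.

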## **RISKS.**

Participation in this study does not imply an increased risk since it is a cross-sectional study, which will not interfere with the daily activities of the center in terms of clinical and therapeutic management of patients. The study will be carried out in accordance with local regulations and applicable laws and following internationally accepted ethical standards.

## **CONFIDENTIALITY OF THE INFORMATION COLLECTED IN THE CONTEXT OF THE STUDY.**

The study research staff will ensure that the pseudonymization of participants is maintained. Which will be identified through a code in the electronic database, with all their information associated with this code and not with their personal data. This database will be stored on a service computer, access to which is password protected. Additionally, the database will also be protected by a password. This information will be stored securely and will only be accessible to members of the research team and authorized personnel.

The questionnaire to obtain the data will use the Microsoft Form platform and when the information is provided to the research team it will be coded and pseudonymized, making it untraceable and respecting the privacy of the data provided.

The person responsible for the processing and custody of the data will in all cases be the principal investigator of the study.

At the end of the study, the data will be stored in the institutional online repository of the Department of Health and Sergas RUNA for a minimum of 10 years, under a password that only the main researcher will have access to in Excel format that will be protected with a different password. also with only access for the main researcher.

In the future, if these data are required for subsequent studies, consent must be sought from the principal investigator.

## **COMMITMENT TO PUBLISH RESULTS**

Researchers must make the commitment to make the results of their research public, whether positive or negative.

## **ECONOMIC REPORT AND SOURCE OF FINANCING**

This project does not have financing.

## **ANNEXES**
